### 1.6. Changes to Planned Analysis

Additional details were added for several exploratory endpoints.

Moreover, all RT-PCR confirmed RSV cases, during the first RSV season will be evaluated by a Clinical Evaluation Committee (CEC) and classified as mild, moderate, or severe RT-PCR confirmed RSV-mediated diseases. See CEC Charter (EDMS-ERI-51904526) for further details on the CEC responsibilities. Based on the CEC evaluation the following exploratory endpoints were added:

- first occurrence of an RT-PCR confirmed RSV LRI assessed as at least mild by the CEC
- first occurrence of an RT-PCR confirmed RSV LRI assessed as at least moderate by the CEC.
- first occurrence of an RT-PCR confirmed RSV LRI assessed as severe by the CEC.

Finally based on EMA comments two additional exploratory endpoints were added to the analysis of the first RSV season.

In comparison to the immunogenicity analysis described in the CTP (Section 11.9.2) for all Revaccination Subcohorts (and not only for Revaccination Subcohort A with revaccination at day 365) geometric mean ratios and corresponding 95% CIs between Day 15 post first vaccination and Day 15 post second vaccination within the group receiving active study vaccine on Day 1 and

the day of the second vaccination depending on the Revaccination Subcohort will be calculated for the different assays.

Categorical BMI was updated to align with the Phase 3 studies to include the categories ‘< 18.5 kg/m^2’, ‘18.5 to < 25 kg/m^2’, ‘25 to < 30 kg/m^2’ and ‘>= 30 kg/m^2’. Additionally, smoking status was updated. Participants who use used nicotine patches or gum are no longer being considered as a smoker. Details were added to the analyses of analgesics and antipyretics to specify the period assignment if usage begins on day of vaccination.

The fourth sensitivity analysis in Section 4.4.2.2. was updated. The specificity for RSV A for the GenMark assay is 93%-96% and for RSV B its 95%-97% which might result in more false positives compared to GeneXpert (specificity of 99-100%). Therefore, the DDL results were used to determine RSV positivity of the ARI for cases where the results of GeneXpert and GenMark differ.

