##### **4.2.1.1. Definitions**

Solicited AEs shown in the tables and listings will be based on the overall assessment of the investigator. For unsolicited AEs, only the AEs and SAEs within the 28-day period following the vaccination will be presented in the safety tables. SAEs, will be captured and tabulated in outputs covering the whole study period. Unsolicited non-serious adverse events collected outside the 28-day period following the vaccination will be presented through listings. The number of subjects within the Safety subset will be used as a denominator for the solicited and unsolicited AEs, and the number of subjects in the FAS will be used as a denominator for the SAEs. Solicited AEs and unsolicited non-serious AEs should per protocol only be collected for the safety subset. If these would be reported by mistake for non-safety subset subjects, they will be listed separately.

Solicited local AEs will be by definition considered as related to the study vaccine.

The severity of the AEs will be classified as grade 1 to 4. The reporting of solicited AEs will be based on the investigator assessment as document in the CE domain. Solicited events of grade 0, not reported in the CE domain, will therefore not be reported in the AE analysis.

Any ARI recorded as an (S)AE in the eCRF will be excluded from any AE analysis if it is a confirmed RSV infection by RT-PCR (midturbinate swabs and sputum sample, when available) based on the central laboratory or if it is connected with a hospitalized confirmed RSV infection based on an FDA-approved RT-PCR test at the local laboratory.

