#### **4.4.2.1.2. RSV RT-PCR Confirmation of the Considered ARI Episode**

Confirmation of RSV infection by RT-PCR (in midturbinate swabs or sputum sample, whenever available) will be performed at the central laboratory (GeneXpert assay only). For participants hospitalized with symptoms of an ARI, confirmation of RSV infection using an FDA-approved RT-PCR test at the local (hospital) laboratory will also be used for the analysis of case definitions if results from the central laboratory are not available. One positive sample (defined as any sample with a value above the limit of detection) is sufficient. RT-PCR results from samples that were out of stability are excluded from the analysis, regardless if they were RSV positive or RSV negative (except for the analysis based on the FAS).

Any midturbinate nasal swab and/or sputum sample taken within 7 days after onset of an ARI episode or during the ARI episode will be allocated to that ARI. In case of 2 consecutive ARI episodes, where the second ARI starts within 7 days after the onset of the first episode and the ARI Day 3-5 sample of the first episode is taken while the second episode is ongoing, then the midturbinate nasal swab and/or the sputum sample will be attributed to both ARIs.

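### The adverse-event exclusion accepts a local RSV test even when the central test is negative, so a hospitalised ARI can be absent from both the SAE tables and the RSV case counts

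*SAP*

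**What the plan says.** **Safety rule (SAP 4.2.1.1).** "Any ARI recorded as an (S)AE in the eCRF will be excluded from any AE analysis" on two alternative grounds. The first is RSV confirmation "by RT-PCR (midturbinate swabs and sputum sample, when available) based on the central laboratory". The second ground, for hospitalised cases, reads: "or if it is connected with a hospitalized confirmed RSV infection based on an FDA-approved RT-PCR test at the local laboratory". Either limb is enough. The rule names no central assay and sets no condition on sample stability. It does not require the central result to be missing, and it does not refer to Section 4.4.2.1.2.

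**Efficacy rule (SAP 4.4.2.1.2).** Central confirmation rests on GeneXpert alone. For hospitalised participants the local test "will also be used for the analysis of case definitions if results from the central laboratory are not available". On stability: "RT-PCR results from samples that were out of stability are excluded from the analysis, regardless if they were RSV positive or RSV negative", with the FAS-based analysis as the one exception. A swab or sputum sample counts for an episode if "taken within 7 days after onset of an ARI episode or during the ARI episode will be allocated to that ARI".

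Sections 4.4.3.1 and 4.4.4.1 add notes that RSV confirmation for the secondary and exploratory endpoints is by GeneXpert only.

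**The concern.** Leaving confirmed RSV illness out of the AE tables of an RSV vaccine trial makes sense when that illness is counted as an efficacy outcome instead. That works only if both sides use the same definition of confirmed. Here the safety side is wider. Where the two rules disagree, the same serious respiratory illness is treated as RSV when the SAE table is built and as not RSV when cases are counted.

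At stake is the completeness of the SAE table, which Section 4.2 bases on the entire FAS, for hospitalised respiratory illness. Section 3.1 names Sections 4.2, 4.4.1 and 4.4.2 as those that apply to the IDMC analyses, so the committee's tables carry the same gap.

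**Working it through.** The SAP gives no figure to reproduce, and no arithmetic applies. The check sets the two rules side by side and follows a serious ARI through them.

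| Condition | AE exclusion (4.2.1.1) | Efficacy confirmation (4.4.2.1.2) |
|---|---|---|
| Local hospital RT-PCR positive | Sufficient by itself | Used only if no central result is available |
| Central assay | Not named | GeneXpert only |
| Out-of-stability sample | Not mentioned | Not used, except in the FAS analysis |

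**Outcome by test result**

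1. *Valid central GeneXpert positive.* Removed from AE analyses and confirmed as RSV for efficacy. The rules agree.
2. *Local positive, no central result.* Removed from AE analyses and confirmed for the primary analysis. The rules agree there.
3. *Local positive, valid central GeneXpert negative.* Removed from AE analyses by the local limb. Not confirmed for efficacy, because a central result exists. The rules disagree.
4. *Only positive is a central sample out of stability.* Removed from AE analyses as the text reads. Absent from the PPE counts, but present in the FAS sensitivity analysis (4.4.2.2, and 5.4.1.2 for later seasons).

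**Does any efficacy analysis recover result 3 as RSV?**

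- Primary PPE analysis: no, by 4.4.2.1.2.
- FAS sensitivity analysis (4.4.2.2): no. It adds out-of-stability positives and early-onset cases, and does not change the condition on the local test.
- Multiple imputation (4.4.1.2): no. Nothing is imputed once a single RT-PCR test is available.
- Secondary and RSV-linked exploratory endpoints: no, under the GeneXpert-only notes. Table 9 labels the ordinal definition as GeneXpert or local laboratory without a condition, but it also maps each level to Case Definitions 1 to 3, which follow 4.4.2.1.2.
- GenMark sensitivity analysis (4.4.2.2): only if GenMark and DDL are both positive, and only if GenMark is available for all ARIs.

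**Where result 3 can still be seen in season 1**

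- First hospitalisation and first complication linked to any ARI, neither of which needs RSV confirmation (4.4.4.1, 4.4.4.2).
- Resource-use summaries for RSV-negative ARIs (4.11.1).
- Listings or narratives for serious AEs, provided as appropriate (4.2.1.2).

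**Where most of these views are missing**

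- IDMC: the any-ARI endpoints and the resource-use summaries lie outside Sections 4.2, 4.4.1 and 4.4.2.
- Seasons 2 and 3: Section 5.2 carries the safety approach forward. Section 5.4.1.1 lists hospitalisation and complications only when linked to RT-PCR-confirmed RSV, and Section 5.10.1 ties emerging resource use to confirmed RSV. From Day 365, Section 5.2 also makes ARI-associated SAEs one of a limited set of SAE types still collected for participants who are not revaccinated.

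**The case against.** The best defence is that the two rules serve different purposes. A strict primary endpoint and a safety attribution need not share a definition, and a hospitalised patient with a positive FDA-approved test has plausibly had the disease under study. The wording of 4.2.1.1 also follows 4.4.2.1.2 closely and may simply abbreviate it. Both arguments are fair. But the SAP gives no reason for a wider safety rule, and if abbreviation was meant, the dropped condition is the one that decides result 3. One might also point to the statement in 4.4.2.1.2 that one positive sample is enough. That follows the condition on the local test and does not cancel it.

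Three stronger readings are tempting and are not supported.

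- *That every discordant serious ARI disappears altogether.* Out-of-stability positives return in the FAS sensitivity analysis, and season 1 has the any-ARI endpoints described above.
- *That a lone GenMark or DDL positive removes an SAE.* Section 4.2.1.1 does not name the assay, so this is not ruled out. The more natural reading is GeneXpert, given 4.4.2.1.2 and the notes in 4.4.3.1 and 4.4.4.1.
- *That the GenMark specificities in Section 1.6 size the loss.* Such a calculation needs that less natural reading, independent errors for RSV A and B, and a number of serious non-RSV ARIs that the SAP does not give. Section 4.4.4.1 also says that running GenMark on all ARIs was not yet planned for the primary analysis. No rate from it should be used.

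**Conclusion.** The point holds for one clearly defined group: hospitalised ARIs recorded as (S)AEs that are local positive and central GeneXpert negative. They leave the AE and SAE tables as RSV and are not counted as RSV in the primary, FAS sensitivity, secondary or RSV-linked exploratory analyses. This follows from the text and needs no assumption beyond the existence of such a discordant pair.

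The missing GeneXpert-only and in-stability conditions in 4.2.1.1 are a secondary point. For stability the effect is confined to the PPE counts.

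The number of events is not derivable and is probably small. The SAP gives no basis for saying which group would be favoured. The matter still deserves correction, because it decides which serious events enter the SAE tables, including those for the IDMC and for seasons 2 and 3, where most of the other views of such events are absent.

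**What to change.** In Section 4.2.1.1, replace the two-part criterion with a cross-reference: an ARI recorded as an (S)AE is excluded from AE analyses only if it is RT-PCR-confirmed RSV according to Section 4.4.2.1.2, that is, by central GeneXpert on an in-stability sample, or by the local test only when no central result is available. State that all other ARI (S)AEs stay in the tables, and add a listing by group of every excluded event. The listing would also show excluded events in participants outside the PPE, which the new wording would still remove from the tables.

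The cost is a sentence, a listing and reuse of the efficacy confirmation flag in the AE dataset. No endpoint, alpha level or sample size changes. The SAE count may rise by a few events. Out-of-stability positives would then appear both in the SAE tables and in the FAS sensitivity analysis, which a footnote can explain.

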##### **4.2.1.2. Analysis of Adverse Events**

Number and percentage of subjects with at least one particular AE (unsolicited/solicited) will be tabulated. Unsolicited AEs and SAEs will be summarized by System Organ Class and Preferred Term. Solicited AEs will be summarized by class (local, systemic) and preferred term.

For solicited AEs following tables will be provided: summary, by worst severity grade, at least grade 3, related (systemic only), time to onset (in days) and duration (in days) for all events and body temperature.

Note 1: Body temperature will be summarized based on the participants measurements.

Note 2: Duration is defined as number of days from the start of the event until resolution of the event. The time to first onset is defined as (date of first onset – reference date + 1). The reference date is the start date of the vaccination period.

For unsolicited AEs following tables will be provided: summary table (including SAE, fatal outcome, and discontinuation), all events, most frequent, grade 3, permanent stop of vaccine and related.

For SAEs following tables will be provided: all events and all related events.

Listings and/or subject narratives will be provided as appropriate, for those subjects who die, discontinue study vaccinations due to an AE, or experience a severe or serious AE.

#### **4.2.1.3. Phase allocation of Adverse Events**

As the analysis of solicited events will be based on the overall assessment of the investigator which is documented in the CE domain, ADAMs will be based on CE. Solicited events are allocated to the phases as described below, however they are always allocated to the respective post-dose period and will never be attributed to the screening phase. Time is not considered while attributing solicited AEs to phases.

For unsolicited AEs, the steps below are followed as well.

##### **Step 1: Allocation of events to the periods:**

Adverse events in the SDTM database are allocated to periods based on their start date/time.

- If the start date/time of an event falls between (or on) the start and stop date/time of a period, the AE is attributed to that period (emergent principle).
- In case of partial start or stop dates (i.e. time and/or day and/or month and/or year missing), the events are allocated to the periods using the available partial information on start and end date; no imputation will be done. If, for instance, the AE start date only month and year are available, these data are compared to the month and year information of the periods. This rule may lead to multiplication of the event as a consequence of its assignment to multiple periods.
- In case of a completely missing end date, the date is imputed by the cut-off date of the analysis for subjects still ongoing in the study, and by the end date of the last phase for subjects who discontinued or completed the study.
- In case of a completely missing start date, the event is allocated to the first active treatment phase (post dose 1 period), except if the end date of the AE falls before the start of the first active treatment phase (post dose 1 period).

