**Table 2: Phase Definitions all subjects (excluding revaccination periods)**

Phase	Phase #	Period	Period #	Interval	
				From	To
Screening	1			Date and time of signing the informed consent form	One minute prior to start of post dose 1 period
Regimen	2	Post-dose	1	Date and time of first vaccination	Minimum of: 
 
a) 23:59 at the date of last contact (for early discontinuation from study)
 
b) 23:59 at the date of database cut-off date
 
c) Maximum (28 days after first vaccination at 23:59, scheduled visit 4 weeks after first vaccination at 23:59)
 

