## 5.2. SAFETY

Safety analyses for the second and third RSV season will be performed similarly to the first RSV season (see Section 4.2), based on the FAS. The analysis of solicited and unsolicited AEs will be restricted to the Revaccination Subcohorts.

For the analysis of serious AEs (SAEs) the entire FAS will be used. **For participants who will not receive a revaccination**, all SAEs will be reported from administration of study vaccine on Day 1 until the end of the first RSV season (or 6 months after vaccination, whichever comes later). In addition, SAEs classified as related to the study vaccine, SAEs resulting in death, (S)AEs resulting in study discontinuation, and (S)AEs resulting from procedures and non-investigational (concomitant) Janssen products will be collected during the entire study for all participants. For these participants, SAEs associated with ARIs and complications related to ARIs that classify as SAEs will be collected from the Day 365 (Month 12) visit until the end of the second RSV season, from the end of the second RSV season until the Day 730 (Month 24) visit, and from the Day 730 (Month 24) visit until the end of the third RSV season.

In the Revaccination Subcohorts B, C and D from 1st revaccination onwards and in Revaccination Subcohort 2A from d730 onwards, thrombosis with thrombocytopenia syndrome (TTS) is to be reported to the sponsor as an adverse event of special interest (AESI), within 24 hours of awareness. A potential AESI is defined as thrombotic events or symptomatic thrombocytopenia. For the analysis of serious AEs (SAEs) and (potential) AESIs in the Revaccination Cohorts the FAS will be used as well.

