Potential AESIs (programmed/identified by the investigator) that have risk levels assessed by one of the following three criteria are considered ‘qualified for assessment’:
  - Brighton Collaboration Level (Level 1-5)
  - CDC Tier (non-tier 1/2, tier 1, tier 2)
  - PRAC criteria (confirmed, possible, probable, unlikely, criteria not met)

As AESI (potential, identified by the investigator and/or qualified for assessment) are only collected in the Revaccination Subcohorts B, C and D from 1st revaccination onwards and in Revaccination Subcohort 2A from Day 730 onwards, the analysis of these potential AESI will only include these cohorts/timepoints. Potential AESIs as identified by the investigator, will be tabulated according to the following categories: ‘Embolic and thrombotic events (SMQ; Standardised MedDRA Queries)’ and ‘Haematopoietic Thrombocytopenia (SMQ) (broad) or HLT (higher level term) = ‘Thrombocytopenias’, and ‘Other’. Potential AESI as identified by the investigator, related to study vaccine (investigator assessment), will be tabulated similarly. Potential AESIs qualified for assessment will be tabulated by categories: ‘Embolic and thrombotic events (SMQ)’ and ‘Haematopoietic Thrombocytopenia (SMQ) (broad) or HLT=Thrombocytopenias’.

In addition to the potential AESIs as identified by the investigator in the database, potential AESIs will also be selected programmatically. Those will be tabulated by categories: ‘Embolic

and thrombotic events (SMQ)' and 'Haematopoietic Thrombocytopenia (SMQ) (broad) or HLT=Thrombocytopenias'. Potential AESI determined programmatically, related to study vaccine (investigator assessment), will be tabulated similarly. For these, all cohorts and the whole study period will be included in the analyses.

All AESI analyses will be presented by phase as well as by time interval. The definition of the different time intervals can be found below.

Dose	Interval	From	to
Post-vaccination 1	0-28 days post-dose	Date time of the 1 st vaccination	Min of: * 
 
• 23:59 at the date of last contact (for discontinuations)
 
• 23:59 at date of DB cut-off for interim analyses
 
• Maximum (Date of Vaccination 1 + 28 days at 23:59 , date of scheduled visit 4 weeks after 1st vaccination at 23:59)
 

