In case the definitions of the time intervals cause overlap, the start date of the latter time interval should always start one minute after the end of the previous one.

For potential AESIs qualified for assessment, potential AESIs as identified by the investigator and potential AESIs determined programmatically, attribution to the intervals will be done similarly to the unsolicited AEs as described in Section 4.2.1.3. For Step 2 of phase allocation of adverse events, the '0 - 28 days post-dose' interval should be treated similar to 'active' periods and the rest as 'non- active' periods.

Further, for solicited AEs, the denominator for the percentages will be the number of participants with data assessed by the PI in the considered population and phase for a certain regimen (incidence per 100 participants/phase) and risk level.

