### 5.3. Immunogenicity Analysis

The analysis of immunogenicity will use the PPI set. For both the Immuno subset and the Revaccination Subcohorts, the immunogenicity analysis will follow the analysis outlined in Section 4.3. Except for Revaccination Subcohort B, Post-F ELISA results will no longer be assessed from Day 365 onwards for the Immuno Subset and Revaccination Subcohorts A, C and D.

In addition, for each Revaccination Subcohort separately, geometric mean ratios and corresponding 95% CIs between Day 15 post first vaccination and Day 15 post second vaccination within the group receiving active study vaccine on Day 1 (group 1A, 1B, 1C and 1D respectively) will be calculated for the different assays.

Moreover, the GMT ratios with corresponding 95% CIs of Day 15 post second vaccination for the group receiving active study vaccine twice versus the group receiving placebo first and active study vaccine 1, 2, 3 or 4 years later will also be calculated for the different assays. Therefore, an analysis of variance (ANOVA) model will be fitted with the respective titers as dependent variable and group as independent variable. The point estimate and CIs obtained as such will be back transformed (by exponentiation) to a GMT ratio and the corresponding CI. As a sensitivity analysis, different variances between the groups will be allowed, therefore the CIs will be calculated via Welch's ANOVA.

A similar analysis might be performed at other timepoints as well.

For Revaccination Subcohorts 2A and 2B that get a third vaccination with Ad26.RSV.preF/RSV preF protein mixture or with the individual vaccine components, no formal hypothesis is tested; descriptive statistics over time after the third vaccination will be calculated.

Graphical representations of immunogenicity parameters will be made as applicable.

The impact of baseline factors on the humoral responses will be explored graphically or via descriptive statistics.

Note that tables including descriptive statistics of actual values and fold changes (if applicable) over time might also once be calculated restricted to participants who have data at the last scheduled timepoint included in the respective analyses of the immunosubset and Revaccination Subcohorts. This might also be graphically shown.

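### The rule that places an event with a completely missing start date in the post-dose 1 period is carried into the revaccination analyses, where dose 1 was placebo for Subcohorts 2A-2D

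*SAP*

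**What the plan says.** Section 4.2.1.3, Step 1, deals with incomplete dates in two ways.

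- **Partial start date:** the event goes to every period that matches the known date parts, and the SAP accepts that it may then appear in more than one period.
- **No start date at all:** "In case of a completely missing start date, the event is allocated to the first active treatment phase (post dose 1 period"). The one exception is an event that was already over when that period began.

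Table 2 starts the post-dose 1 period at "Date and time of first vaccination". Table 1 shows that this vaccination was placebo for Subcohorts 2A-2D, which Section 5.3 describes as "the group receiving placebo first and active study vaccine 1, 2, 3 or 4 years later".

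Section 5.2 then extends the first-season rules: "Safety analyses for the second and third RSV season will be performed similarly to the first RSV season (see Section 4.2"). For all three kinds of potential AESI, "attribution to the intervals will be done similarly to the unsolicited AEs as described in Section 4.2.1.3". It gives no other rule for a missing start date.

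The AESI analyses differ in scope. For investigator-identified and qualified potential AESIs, limited to B, C and D from first revaccination and 2A from Day 730, "the analysis of these potential AESI will only include these cohorts/timepoints". For programmatically selected ones, "For these, all cohorts and the whole study period will be included in the analyses".

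**The concern.** With a single vaccination, placing an undated event right after that vaccination is the cautious choice, because the event counts against the vaccine. With a second or third dose one to four years later, the same rule can do the reverse. The rule ignores an end date after revaccination, the dose that the report followed, and what was injected on Day 1.

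The revaccination part is there to describe the safety of repeat doses in small groups. An allocation rule that can only take undated events out of the repeat-dose periods, and in half of the subcohorts puts them under placebo, works against that aim. It is also inconsistent with the partial-date rule: an event with some date information is spread over all matching periods, while an event with none is tied to a single period.

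**Working it through.** No figure in the SAP needs reproducing. The check traces the rule and then sizes one event.

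**1. Meaning of the rule.** The phrase on the first active treatment phase might be read as the first phase on active vaccine. The SAP's own parenthesis names the post-dose 1 period, Table 2 starts that period at the first vaccination, and Step 2 of Section 4.2.1.3 uses active period for a post-dose period in general. The rule therefore points to Day 1, whatever was injected.

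**2. A traced case.** Take a participant in 2B: placebo on Day 1, active mixture at Month 24. An event has no start date and an end date after Month 24. The exception does not apply, because the event did not end before Day 1. A missing end date gives the same result, since Step 1 imputes it with the cut-off date or the end of the last phase. The event goes to post-dose 1.

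**3. Where it then appears, by type of event.**

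| Undated event, ended or ongoing after revaccination | Result in 2A-2D |
|---|---|
| SAE (collected in all participants; analysed on the FAS) | In the SAE table up to revaccination, under placebo; absent from the subcohort table that starts at revaccination |
| Programmatically selected potential AESI | In the 0-28 day interval after vaccination 1, under placebo |
| Non-serious unsolicited AE, Safety Subset member | Tabulated under placebo after dose 1 |
| Non-serious unsolicited AE, not in the Safety Subset | Sections 2.3.1, 4.2 and 4.2.1.1 leave it to listings; it drops out of the tables |
| Investigator-identified or qualified potential AESI | Falls outside its own analysis window, which starts at revaccination (Day 730 for 2A) |
| Solicited AE | Not affected; Section 4.2.1.3 keeps it with its own dose |
| Any event with a partial start date | Not affected; a different rule applies |

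In 1A-1D both doses are active. The event moves from the repeat dose to the first dose, not to placebo.

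**4. Participants in scope (planned, Table 1).** 2A + 2B + 2C + 2D = 120 + 135 + 120 + 120 = 495, and the same number in 1A-1D. C and D depend on the Subcohort B results (Table 1, note d). With A and B only, it is 120 + 135 = 255 per first-dose group.

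**5. Weight of one event (1/n).**

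- Subcohort of 120: 1/120 = 0.8 percentage points.
- Subcohort of 135: 1/135 = 0.7 percentage points.
- Third-dose arm of 40 (2A): 1/40 = 2.5 percentage points.
- Third-dose arm of 45 (2B): 1/45 = 2.2 percentage points.

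The SAP gives no expected number of events with a completely missing start date, so the total effect cannot be computed.

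**The case against.** The strongest case on the other side has four parts.

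- **The trigger is narrow.** The start date must lack day, month and year. Because revaccination follows dose 1 by one to four years, even a known year will often rule out post-dose 1. TTS must be reported within 24 hours of awareness, so a wholly undated report of it is unlikely. This stands, and it limits the size of the point.
- **Not everything is counted under placebo.** A reader might infer that every undated AE or AESI after revaccination is credited to placebo. The documents do not support that. Solicited AEs are exempt, non-serious AEs outside the Safety Subset go to listings, and two of the three AESI categories have no placebo period in their analysis. This stands. In the last two situations, however, the event is still missing from the tables or in conflict with its own window.
- **Similarly is not identically.** Section 5.2 uses the looser word, so the programmers could adapt the rule. This is weak. Section 5.2 does say how Step 2 is to be adapted to the AESI intervals and says nothing about Step 1.
- **The onset is unknown.** An undated event that ended after revaccination may have begun earlier, so one cannot say that it truly belongs to the active dose. This is correct. The fault is that the rule settles the uncertainty in one direction, towards dose 1, even when the record does not.

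A remedy based only on when the event was first recorded would also misplace events. For C and D, Section 5.2 has certain (S)AEs collected retrospectively on the day of revaccination, so an older event could be given to the new dose.

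**Conclusion.** Wrong as written, and minor. The SAP states a rule that can place an undated event under placebo in 2A-2D when onset after an active dose has not been excluded. This holds for SAEs, programmatically selected potential AESIs and Safety Subset unsolicited AEs. Other undated non-serious AEs and AESIs drop out of the tables or fall outside their analysis window, and in 1A-1D the event moves to the first dose.

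The size is 0.7-0.8 percentage points per event in a subcohort and 2.2-2.5 in a third-dose arm. This assumes the planned numbers and that C and D go ahead. The number of such events is not given and is probably small.

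A reader might go further and infer that the repeat-dose safety results are materially biased in favour of the vaccine. The documents give no count that would support this. The point concerns an analysis convention and touches no clinical management rule.

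**What to change.** Add to Section 5.2, as an override of Section 4.2.1.3 Step 1 for revaccinated participants:

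- An event with a completely missing start date is allocated to every period that is not excluded by its end date, by the collection window, or by other recorded information. The last includes the fact that an event in C or D was collected retrospectively for the time before revaccination.
- Such an event is not allocated to the placebo post-dose 1 period alone when onset after an active dose cannot be excluded.

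State that the same applies to the AESI time intervals, so that investigator-identified and qualified events are not lost from their own analysis.

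The cost is about a sentence in the SAP and a small change in the allocation program. The downside is that one event may be counted under more than one dose. The SAP already accepts this for partial dates, and a footnote giving the number of events so allocated would make it visible.
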